8.1.1 Randomization	13
8.1.2 Blinding	14
8.2 DATA COLLECTION AND MANAGEMENT	14
8.3 CONFIDENTIALITY	14
8.4 REGULATORY AND ETHICAL CONSIDERATIONS	15
8.4.1 Data and Safety Monitoring Plan	15
8.4.2 Risk Assessment	15
8.4.3 Potential Benefits of Trial Participation	16
8.4.4 Risk-Benefit Assessment	16
8.5 RECRUITMENT STRATEGY	16
8.6 INFORMED CONSENT/ASSENT AND HIPAA AUTHORIZATION	17
8.7 PAYMENT TO SUBJECTS/FAMILIES	18
8.7.1 Reimbursement for travel, parking and meals	18
8.7.2 Payments to subject for time, effort and inconvenience (i.e. compensation)	18
9 PUBLICATION	18
10 REFERENCES	18
Appendix	21

ABBREVIATIONS AND DEFINITIONS OF TERMS

ED	Emergency Department
AE	Adverse event
SAE	Serious adverse event
STAT-ED	Suicidal Teens Accessing Treatment
RCT	Randomized Controlled Trial
CBC	Congressional Black Caucus
EHR	Electronic Health Record
BHS	Behavioral Health Screen
ADAPT-ITT	Assessment, Decision, Administration, Production, Topical Experts and Integration, Training, and Testing
MYTS	Motivation for Youth's Treatment Scale
SIQ-Jr	Suicide Ideation Questionnaire-Junior
PANAS	Positive and Negative Affect Scale
ICD	International Classification of Diseases, Functioning and Disability
NDA	NIMH Data Archive
NIH	National Institutes of Health
DSMB	Data Safety and Monitoring Board
AIM	Acceptability of Intervention Measure
ED STARS	Emergency Department Screen for Teens at Risk for Suicide
FIM	Feasibility of Intervention Measure

ABSTRACT

Context:

Recent research has shown significant increases in suicides among Black youth and suicide attempts among Black high school students.

Objectives:

Primary

- To conduct a systematic adaptation of STAT-ED for Black youth presenting in the ED who have suicidal risk.
- To examine preliminary efficacy of the intervention on primary (mental health treatment initiation and number of visits) and secondary (suicidal ideation) outcomes using a prospective RCT design.

Secondary

- To examine implementation outcomes of the adapted STAT-ED for Black youth and caregivers compared to the control condition (enhanced Treatment as Usual).

Study Design:

The study utilizes a mixed methods design which involves a qualitative phase (interviews and field testing) and RCT phase.

Setting/Participants:

The study will recruit from CHOP pediatric hospital ED with a total of 151 participants (75 youth, 75 caregivers, and 1 patient navigator). Eligible youth will identify as Black, be between the ages of 10-18, have recent or past suicidal ideation or behaviors and are not currently receiving mental health treatment. Caregivers are parents or legal guardians of eligible youth. Patient navigator will be hired patient navigator who consents to being a secondary research participant. Study procedures may be conducted in-person, over the phone, or online.

[figure not shown]
Study Interventions and Measures:

Participants will be randomized to the adapted STAT-ED or enhanced Treatment as Usual which will consist of follow up telephone contacts following discharge from the ED. Main RCT study outcomes are mental health treatment initiation and suicidal ideation.

Table 1: Schedule of Study Procedures for Randomized Controlled Trial

Study Phase	Screening	Observation Study Visits		
Visit Number		Baseline	2 month follow up	6 month follow up
Informed Consent/Assent	X			
Review Inclusion/Exclusion Criteria	X	X		
MYST		X	X	X
SIQ-Jr		X	X	X
Demographics		X		
PANAS		X		
AIM			X	X
ED STARS			X	X
Adverse Event / Unanticipated Problems Assessment		X	X	X

Figure 1: Flow Diagram for RCT

1 BACKGROUND INFORMATION AND RATIONALE

1.1 Introduction

Suicide is the second leading cause of death among 10-24 year olds, and suicide rates are increasing (Curtin & Heron, 2020). Historically, Black youth have had lower suicide risk; however, recent research has shown disturbing and significant increases over the last 3 decades in suicides among Black youth and in self-reported suicide attempts among Black high school students (Sheftall et al., 2016; Bridge et al., 2015; Bridge et al., 2018; Ivey-Stephenson, 2020; Lindsey et al., 2018). Black youth are less likely than White youth to be treated for suicidal ideation or behaviors, and less likely to receive inpatient or outpatient care after a suicide attempt (Freedenthal, 2007; Marrast et al., 2016). Barriers to Black youth starting mental health treatment are myriad and include lack of perceived need, stigma, mistrust of providers and treatment, difficulties in physically accessing available services, and providers' lack of cultural competence (Fante-Coleman & Jackson-Best; Planey et al., 2019). Patient navigation offers a flexible model that can address many of these barriers and can be tailored to specific populations and needs. Although patient navigation models have been shown to improve outcomes such as screening and diagnostic appointment and referral completions in different patient populations (Ali-Faisal et al., 2017), there is paucity of such interventions and associated research to improve care and outcomes for suicidal youth. One of these patient navigation interventions, Suicidal Teens Accessing Treatment (STAT-ED) resulted in greater mental health care initiation and appointment at 6 months, however, adolescents of color were less likely to initiate mental health care than White adolescents (Grupp-Phelan et al., 2019). An intervention for Black youth requires adaptation, as many interventions do not address culturally relevant issues for Black patients. This proposed study will adapt and pilot test STAT-ED for Black youth presenting to emergency departments (EDs) with suicidal ideation or behaviors.

1.2 Name and Description of Investigational Product or Intervention

Patient navigation will generally be modeled after STAT-ED and can involve motivational interviewing, brief case management, and telephone contacts. While the complete intervention is contingent on our adaptations, we anticipate that the following strategies will be included: psychoeducation, problem-solving logistical barriers, and assistance with making and following up with mental health appointments (Godoy et al., 2019). As part of the cultural adaptation, we will directly address youth's and caregivers' negative perceptions and cultural stigma concerning mental health treatment. Psychoeducation will be provided on suicide risk, its negative effects, and treatment options. The intervention will assist the family in following up with mental health referral recommendations provided by ED staff and eliciting families' preferences in regards to race and gender of providers, convenience of provider, and type of treatment. This assistance could involve help with the initial telephone contact, getting to appointments, and preparing for the appointments. The patient navigator will communicate with the family in person, by telephone, and/or by text messaging as per family's preference. This once to twice a week communication will promote mental health care initiation and identify barriers and problem-solving solutions. The intervention group is expected to be administered the adapted STAT-ED until the first mental health appointment

date. A comparison intervention (enhanced Treatment as Usual) will consist of follow up contacts following discharge from the ED to confirm referral recommendations.

1.3 Relevant Literature and Data

A systematic review of interventions that attempted to increase initiation of mental health care for people of color found that most were culturally adapted. Adaptations included incorporating racially diverse perspectives in intervention design, training staff on cultural sensitivity issues, referencing racial/ethnic diversity in educational materials, and incorporating cultural conceptualizations of mental health (Lee-Tauler et al., 2018). A similar systematic review of psychosocial mental health interventions for youth of color found that all interventions shown to be efficacious were culturally adapted (Pina et al., 2019), and a third review supported cultural adaptations of interventions for mental health care engagement among adolescent and young adults of color (Moore, 2018). Although there are not substantial data indicating that culturally adapted interventions are more effective, in the mental health intervention field, the clear disparity in engaging Black individuals strongly suggests that current approaches may not be sufficient. The CBC Taskforce report on Black youth suicide and mental health (2019) further emphasizes this point, recommending that researchers develop and test interventions to mitigate suicide risk that are developmentally, culturally, and linguistically relevant for Black youth. We will adapt a patient navigation intervention, the STAT-ED for Black youth with suicide risk, following the ADAPT-ITT framework steps of Assessment, Decision, Administration, Production, Topical Experts and Integration, Training, and Testing (Wingood et al., 2008). This will involve data from qualitative phases of study, as well as input for advisory group and consultants.

1.4 Compliance Statement

This study will be conducted in full accordance all applicable Children's Hospital of Philadelphia Research Policies and Procedures and all applicable Federal and state laws and regulations including 45 CFR 46. All episodes of noncompliance will be documented.

The investigators will perform the study in accordance with this protocol, will obtain consent and assent, and will report unanticipated problems involving risks to subjects or others in accordance with The Children's Hospital of Philadelphia IRB Policies and Procedures and all federal requirements. Collection, recording, and reporting of data will be accurate and will ensure the privacy, health, and welfare of research subjects during and after the study.

2 STUDY OBJECTIVES

The purpose of the study is to determine the efficacy of the adapted STAT-ED patient navigation intervention for Black youth initiation of mental health treatment.

2.1 Primary Objective (or Aim)

- To conduct a systematic adaptation of STAT-ED for Black youth presenting in the ED, who have suicidal risk.
- To examine preliminary efficacy of the adapted STAT-ED on primary (mental health treatment initiation and number of visits) and secondary (suicidal ideation) outcomes using a prospective RCT design.

2.2 Secondary Objectives (or Aim)

The secondary objectives are to:

- To examine implementation outcomes of the adapted STAT-ED intervention (acceptability, feasibility, fidelity) for Black youth and caregivers compared to the control condition (enhanced Treatment as Usual).

3 INVESTIGATIONAL PLAN

3.1 General Schema of Study Design

The study utilizes a mixed methods design which involves a qualitative phase and randomized trial phase. The qualitative phase consists of two steps: 1) interviews with 15 youth and 15 caregivers and 2) field testing of the intervention with 5 youth and 5 caregivers. The qualitative phase and field testing will occur prior to the randomized trial. The randomized trial is a prospective design comparing adapted STAT-ED with comparison condition. We will test the adapted patient navigation intervention in a small RCT with 50 Black youth presenting in the ED with suicidal ideation or behaviors and their caregivers. The RCT will be conducted after an amendment to the study is approved by the IRB. Medical and mental health information will be collected from medical records.

Caregiver and youth interviews will be conducted separately and virtually either over the telephone or through a CHOP approved virtual meeting platform, either Blue Jeans or Microsoft Teams. Interviews will be recorded. We will incorporate feedback from the youth and caregiver qualitative interviews as well as elicit feedback on which intervention components will be adapted and the types of cultural adaptations needed from the study Advisory Group (caregivers, youth, and clinicians) and a consultant.

During the field testing, we will conduct as rapid-cycling prototyping and testing to gather information on intervention content, materials, and delivery. This will involve conducting the intervention, examining recruitment strategies and gaining more information about mental health referral strategies.

3.1.1 Screening Phase

For the qualitative interviews, the field testing, and the RCT, potential participants will be identified through three avenues in the ED: 1) clinicians; 2) a behavioral health screening conducted in the ED; and 3) diagnostic codes in the electronic health record (EHR). Co-I [name], ED attending physician and ED Behavioral Health Program Director and his team

will identify and recruit potential participants via three avenues: (1) all ED patients aged >12 years complete the Behavioral Health Screen (BHS), which includes a suicidal ideation item; the BHS is on a web-based platform, automatically scored, integrated with patients' EHR, generating automated notification to the ED clinician when the patient reports suicidal ideation. (2) We will peruse the EHR for an extensive list of diagnostic codes related to suicidal ideation, suicide attempt, and self-harm to identify potential participants. (3) ED clinicians can refer patients with suicidal ideation or attempt. Academic Associates, CHOP ED staff whose primary role is to approach potential participants for clinical research, and study staff will screen potential participants using protocol inclusion and exclusion criteria. Academic Associates and study staff will be available in the ED to meet with youth and caregivers, discuss study procedures, enroll participants and gather consent/assent. For participants who meet the study eligibility criteria, we will either gather consent/assent from caregivers and youth in the ED or at a later time by study staff depending on what is convenient for family. If teen and/or caregiver are undecided or do not have time in ED to discuss study, a study flyer will be given by Academic Associates and study staff. Signed consent/assent forms and caregiver and/or youth contact information will be transferred from Academic Associates to study team in a secure manner. Study staff will contact enrolled participants to initiate study procedures for the field testing and RCT and within a week for the interviews.

3.1.2 Study Treatment Phase (start of the study intervention)

Cargiver and Youth Interviews: We developed an interview guide to identify barriers and facilitators to mental health treatment.. We used prompts from our conceptual model to query about issues such as barriers to care that STAT-ED may address, the extent to which STAT-ED components address stigma, and the cultural relevance and appropriateness of STAT-ED components. Interviews were conducted and the audio was recorded by research staff separately for youth and caregivers. All audio files were stored on a secure CHOP server for the study. All audio files were sent to ADA Transcription services for transcription with deletion of any identifying information. The de-identified transcripts were returned and maintained on CHOP's secure research server accessed only by members of the study team. The ADA Transcription services is a CHOP approved vendor that have been used before for other research studies at CHOP and will continue to be used in the future. Initial codes were developed inductively through consensus of the investigative team. Themes pertaining to child and family factors and benefits and barriers to MH service use in a virtual environment were identified. We used EHOST, an open source software program, to facilitate coding of transcripts and identification of themes. The results were used to adapt STAT-ED content and materials in preparation for the RCT. The recruitment for and analyses of the interviews have been completed.

Field testing: We used rapid-cycle prototyping and testing as our field testing. This involved the study staff conducting the intervention and documenting its delivery. This also included examining mental health referral pathways and the study's ability to recruit appropriate patients for the RCT. The study staff provided feedback and observations about the intervention delivery and referral pathways by written notes. We examined screening strategies to identify patients and determine if we are capturing all appropriate patients. The field testing finished recruitment and is complete.

Intervention adaptation: We developed an intervention draft that will balance core elements of the STAT-ED intervention with information gathered from the qualitative interviews and field testing (Wingood et al., 2008). The intervention adaption was informed by the caregiver and youth interviews, and the current literature. We also elicited feedback on which intervention components will be adapted and the types of cultural adaptations needed from the Advisory Group and consultants. This involved using relevant components, as well as writing adaptations to current components and new content. The intervention will include patient navigator instructions, such as motivational interviewing questions, procedures for assisting with mental health appointments, and tips for problem solving barriers, and content for youth and caregivers.. The intervention manual discusses potential intervention delivery strategies such as by telephone, in-person, and by texting. A written manual has been developed.

RCT: Study staff will contact enrolled participants, complete baseline assessments, and randomize to the adapted STAT-ED or control condition (enhanced Treatment as Usual). The adapted STAT-ED will involve the following strategies: psychoeducation, motivational interviewing, problem solving logistical barriers, and assistance with making and following up with mental health appointments. This could involve identifying additional mental health resources and providers based on insurance type. One social worker has been hired and trained to implement the adapted STAT-ED and the control condition (enhanced Treatment as Usual) for study. Patient navigator will communicate with the family in person, by telephone, and/or by text messaging via family's preference. The control condition (enhanced Treatment as Usual) will receive telephone contacts to check in and remind families about mental health care initiation. Telephone contacts are consistent with current ED practice in which social work team members follow up by telephone with patients and their caregivers about referrals given at ED discharge. The proposed study is a small pilot to adapt a patient navigator intervention for suicidal Black youth and test the preliminary effectiveness of the intervention in preparation for a fully-powered RCT. We will perform initial analyses (chi-square and *t*-tests) to compare the intervention and control groups on proportion to initiate mental health treatment, mean number of days to treatment initiation, and mean number of treatment sessions at both 2 months and 6 months follow-up. A Cox proportional hazards model will examine group differences in mental health utilization, time to treatment initiation, suicidal ideation, and mental health motivation (Cox, 1972). Assessments may be conducted in-person, via telephone, or electronically/online. At the end of the study, we will also solicit and review feedback from the patient navigator who is research staff member about feasibility and acceptability. The patient navigator will also complete fidelity measure after first session of the adapted STAT-ED.

Participants may be recontacted to update information or to see if they are interested in participating in other research.

3.2 Allocation to Treatment Groups and Blinding.

In the RCT, subjects will be randomized to either the adapted STAT-ED or to enhanced treatment as usual. Randomization will be accomplished in advance using computer-

generated random numbers. Allocation concealment (blinding of the treatment assignment) will be implemented using sealed, opaque envelopes.

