3.3.2 Total Number of Study Sites/Total Number of Subjects Projected

The study will be conducted at approximately 1 investigative site at CHOP in the United States.

Recruitment for RCT will stop when approximately 100 participants (50 youth-caregiver dyads) are enrolled. It is expected that approximately 100 subjects will be enrolled to produce 85 evaluable subjects. Recruitment for interviews will stop when approximately 30 participants (15 youth-caregiver dyads) are enrolled and recruitment for field testing will stop when approximately 10 (5youth-caregiver dyads) are enrolled.

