5 STUDY EVALUATIONS AND MEASUREMENTS

5.1 Screening and Monitoring Evaluations and Measurements

5.1.1 Medical Record Review

Medical record number

Date of birth

Demographics including county of residence

Race

Columbia Suicide Severity Rating Scale

Behavioral Health Screen

Problem list

ICD codes

Contact information

Languages spoken/read

Results of tests and procedures

Chart review for mental health treatment or hospitalizations (this will be gathered from medical records and will not access protected mental health records)

Medical insurance information

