5.2 Efficacy Evaluations

In the RCT, these are the measures that will be used to assess efficacy (mental health utilization)- ED STARS. The three primary efficacy outcomes are 1) whether the patient initiated mental health treatment (yes/no), 2) time to treatment initiation, and 3) number of

treatment sessions attended. Other outcomes are suicidal ideation and behavior measured by SIQ-Jr.

5.2.1 Diagnostic Tests, Scales, Measures, etc.

In the qualitative interviews, the research staff will conduct semi-structured interviews with questions concerning perceptions and preferences of mental health treatment and barriers and facilitators to accessing mental health services with youth and caregiver participants. In the field testing, participants will not complete any measures or scales. . In the RCT, ED STARS is an interview and will be administered by research staff to caregivers at 2 (Study visit 2) and 6 months (final visit) after baseline assessment. SIQ-Jr is a self-report measure that will be administered to youth at baseline and 2 and 6 months after baseline assessments.

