6 STATISTICAL CONSIDERATIONS

6.1 Primary Endpoint

Primary endpoint for qualitative phase (interviews and field testing): themes of caregiver and youth mental health attitudes and engagement and an adapted STAT-ED manual
Primary endpoint for randomized trial: mental health treatment initiation. The three primary efficacy outcomes are: a) whether the patient initiated mental health treatment (yes/no), b) time to treatment initiation, and c) number of treatment sessions attended.

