6.4 Sample Size and Power

For the RCT, we followed established rules of thumb for pilot trial size estimation for two-armed studies to determine our total sample size of 100 (Whitehead et al., 2016). Even accounting for greater than 15% attrition, power analyses (Faul et al., 2009) indicate that this sample size will produce 80% power to detect a large effect for group differences between conditions over time ($f = .72$). This pilot trial is not intended to detect statistically significant differences in outcomes; rather, the primary aim of this pilot is to establish the feasibility of research procedures in preparation for a fully-powered RCT. The effect sizes obtained in this pilot study will be used to estimate parameters for a subsequent R01 to inform sample size considerations.

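### The 6-month initiation proportion has no rule for youth without a 6-month interview, and the two obvious ways of filling the chi-square table can each bias the difference

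*Combined protocol and SAP*

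**What the plan says.** All references are to the combined protocol and SAP.

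- **Outcome.** Section 6.1 lists three primary efficacy outcomes for the randomised trial: "a) whether the patient initiated mental health treatment (yes/no), b) time to treatment initiation, and c) number of treatment sessions attended". It gives no time point, analysis set or missing-data rule for the yes/no outcome.
- **Test.** Section 3.1.2 plans chi-square and t-tests, called initial analyses, to "compare the intervention and control groups on proportion to initiate mental health treatment" at 2 and at 6 months. It then adds: "A Cox proportional hazards model will examine group differences in mental health utilization, time to treatment initiation". No censoring rule is given.
- **Measurement.** Sections 5.2 and 6.3.2 name ED STARS as the efficacy measure. Under 5.2.1 it "will be administered by research staff to caregivers at 2 (Study visit 2) and 6 months (final visit) after baseline assessment".
- **Loss.** Section 6.4 writes "Even accounting for greater than 15% attrition". Section 3.3.2 expects 85 evaluable subjects from 100. Section 4.4.1 asks withdrawn subjects to complete the later assessments, but has no rule for those who do not.
- **Use of the result.** Section 6.4 says the pilot is not meant to detect significant differences, and that its effect sizes will inform the size of a later, fully powered trial.

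**The concern.** Initiation cannot be undone. A youth reported as a starter at 2 months is a starter at 6 months whether or not the second interview takes place. A youth reported as a non-starter at 2 months and then lost has an unknown 6-month status. Missingness therefore falls unevenly on the two groups, and a chi-square at 6 months needs a yes or no for everyone in the table. The plan does not say where that value comes from.

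The analyst has two easy choices. Keeping only youth interviewed at 6 months discards known starters. Adding back the known starters while leaving the lost non-starters out overstates initiation in whichever arm loses more non-starters. Either can distort the arm difference. The effect size passed to the next trial would then depend on a choice made after the data are seen.

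**Working it through.** **Inputs from the documents.** Section 3.3.2: "Recruitment for RCT will stop when approximately 100 participants (50 youth-caregiver dyads) are enrolled", with 85 of 100 subjects evaluable. That count reproduces: 100 × (1 − 0.15) = 85, or 50 × 0.85 = 42.5 dyads, so about 8 of 50 lost. The documents give no initiation rate and no retention by arm, visit or initiation status. Everything below is therefore assumed, including 1:1 allocation (25 per arm).

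**Notation, per arm.** p2 = proportion started by 2 months. q = proportion of the rest who start between 2 and 6 months. rS and rN = probability of a 6-month interview for 2-month starters and non-starters. All youth are taken as seen at 2 months.

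- True: p2 + (1 − p2)q
- Completers only: [p2·rS + (1 − p2)·rN·q] / [p2·rS + (1 − p2)·rN]
- Known starters carried forward, lost non-starters dropped: [p2 + (1 − p2)·rN·q] / [p2 + (1 − p2)·rN]
- 1 minus Kaplan-Meier: 1 − (1 − p2)(1 − q), with q estimated among 2-month non-starters who are still followed

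**Main scenarios.** p2 = 0.50 (STAT-ED) and 0.25 (control), q = 0.20 in both. Truth: 0.50 + 0.50 × 0.20 = 60% and 0.25 + 0.75 × 0.20 = 40%, a difference of 20 points.

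| Loss pattern | STAT-ED rS / rN | Control rS / rN | Retention | Completers | Carried forward | 1 − KM |
|---|---|---|---|---|---|---|
| A. Differs by arm only | .95 / .95 | .75 / .75 | 95% v 75% | 20.0 | 16.4 | 20.0 |
| B. Control non-starters lost more | .92 / .92 | .92 / .72 | 92% v 77% | 16.1 | 16.4 | 20.0 |
| C. Control starters lost more | .92 / .92 | .65 / .82 | 92% v 78% | 23.3 | 18.5 | 20.0 |
| D. STAT-ED non-starters lost more | .95 / .75 | .85 / .85 | 85% v 85% | 24.7 | 23.2 | 20.0 |

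Row B, control, completers: (0.25 × 0.92 + 0.75 × 0.72 × 0.20) / (0.25 × 0.92 + 0.75 × 0.72) = 0.338 / 0.770 = 43.9%. STAT-ED stays at 60.0%, so the difference is 16.1.

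With no true effect (p2 = 0.30 and q = 0.20 in both arms, so 44% v 44%), the same four patterns give completers' differences of 0.0, −4.3, +3.7 and +4.1. Carry-forward gives −4.2, −4.4, −2.0 and +2.3.

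**A second set of assumed rates.** Initiation by 2 and 6 months is 30% and 45% (control) and 50% and 65% (STAT-ED), so q = 0.15/0.70 = 0.214 and 0.15/0.50 = 0.30. Ten per cent of starters are lost in both arms.

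- Non-starter loss 30% v 15%: control (0.27 + 0.70 × 0.70 × 0.214) / (0.27 + 0.49) = 0.493. STAT-ED (0.45 + 0.50 × 0.85 × 0.30) / (0.45 + 0.425) = 0.660. Difference 16.7.
- Non-starter loss 40% v 20%: control (0.27 + 0.70 × 0.60 × 0.214) / (0.27 + 0.42) = 0.522. STAT-ED (0.45 + 0.50 × 0.80 × 0.30) / (0.45 + 0.40) = 0.671. Difference 14.9.

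**Noise.** In 20,000 simulated trials of 25 per arm under the 40% v 20% case, the SD of the difference was 15.9 points for completers and about 15.4 for Kaplan-Meier, whose mean was about 20.

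**Bounds.** With 2 v 6 lost and 14/23 v 8/19 observed, the difference is 60.9% − 42.1% = 18.8 points. Lost STAT-ED all 'no' and lost control all 'yes': 14/25 − 14/25 = 0. The reverse: 16/25 − 8/25 = 32 points.

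**Effect on the next trial.** Sample size goes roughly as 1/difference². Planning on 16.1 instead of 20 multiplies it by (20/16.1)² = 1.54. Planning on 24.7 multiplies it by (20/24.7)² = 0.66.

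**The case against.** **The plan is silent; it has not made a wrong choice.** A reader might infer that the chi-square can use only youth interviewed at 6 months. The documents do not say so: section 3.1.2 names the test and the time points and restricts nothing. This stands, and the point is confined to the missing rule.

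**Loss by arm.** A reader might also infer that retention will differ by arm in a known direction, because of the contact described in section 1.2: "This once to twice a week communication will promote mental health care initiation". Controls get check-in and reminder calls of unstated frequency. The inference is plausible but unsupported. Navigator contact is expected to end at the first appointment, research staff conduct the outcome interviews, and payments (section 8.7.2) do not differ by arm. Row A also shows that retention differing by arm alone leaves the completers' difference unbiased, while row D shows bias with equal retention. Nor do the documents say how many youth lost by 6 months will have a 2-month report.

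**Existing safeguards.** The Cox model can use 2-month information from youth lost later, once censoring is defined. It estimates a hazard ratio, however, and leaves the proportion difference as it was. Section 5.1.1 also lists "Chart review for mental health treatment or hospitalizations", but that review excludes protected mental health records and is not named as an efficacy measure. The request in section 4.4.1 reduces loss, but the plan still allows for more than 15%.

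**Size.** The bias is small beside an SD near 16. In the second set of rates, root mean squared error was 15.8 (completers) v 14.9 (Kaplan-Meier) at 30% v 15%, and 16.7 v 15.4 at 40% v 20%. This also stands. It limits the weight of the point, but it is no reason to leave the rule open.

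**Conclusion.** The concern holds in a limited form. The plan tests a primary yes/no outcome at 6 months, allows for more than 15% loss, and has no analysis set, missing-data rule, rule for combining the two ED STARS reports, or censoring rule. Where loss is related to initiation status within an arm, a completers-only table was off by 3 to 5 points in the scenarios that combined this with a difference between arms, with either sign. Carry-forward was biased in every row of the table, including the row where completers were not.

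The sizes depend wholly on assumed initiation and loss rates and on full 2-month follow-up. Kaplan-Meier recovers the truth here because loss was made to depend only on arm and 2-month status. The consequence falls mainly on the effect size carried to the next trial, since this pilot is not built for significance testing. It is worth correcting before analysis, and it does not threaten the trial.

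**What to change.** In sections 3.1.2 and 6.3.2:

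1. Estimate the proportion initiated by 2 and by 6 months as 1 minus Kaplan-Meier in all randomised youth, using the days-to-initiation data already planned. Censor non-starters at their last ED STARS interview. If only visit-level status is available, use an interval-censored equivalent.
2. Apply the same censoring rule in the Cox model.
3. Report the difference between arms with a 95% CI at each time point.
4. Keep the complete-case chi-square as a sensitivity analysis and add best/worst-case bounds.

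The cost is analysis-plan wording. One thing to confirm is that start dates will be recorded: the description of ED STARS in section 5.1.2 does not mention them, although mean days to initiation requires them.

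The downside is an assumption that loss is unrelated to later initiation, given arm and status at last contact. Youth lost before 2 months contribute no information, and the bounds show how much that could matter.
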